# **Randomized Controlled Trial of a Sleep Study + Targeted CPAP Therapy for Obstructive Sleep Apnea to Reduce the Incidence of Adverse Pregnancy Outcomes**

**NCT02755831**

**12 February 2016 (IRB Approval Date)**

## **Research Design and Methodology**

A prospective, randomized, parallel group, clinical trial design was used. The treatment group was randomized to receive an unattended WatchPAT-200^18 sleep study in early (6-16wks), late pregnancy (27-33wks), and at 3 months postpartum (between 8 and 12 weeks postpartum). Subjects with an apnea hypopnea index (AHI)  $\geq 5$  were referred to a sleep medicine physician at Naval Medical Center San Diego (NMCS D) for evaluation, education on OSA, and possible initiation of continuous positive airway pressure (auto-titrated CPAP). Subjects randomized to the control group received usual standard prenatal care. Control group subjects completed an unattended sleep study at 3 months postpartum.

Inclusion criteria were at least one of the following risk factors for OSA: pre-pregnancy BMI  $\geq 30\text{kg/m}^2$ , chronic hypertension, pregestational diabetes, twin gestation, or a history of prior pregnancy affected by: preeclampsia, eclampsia or fetal growth restriction. Between 6- and 16-weeks gestation at time of enrollment. Subjects were excluded if they had a current diagnosis and treatment of OSA, refused to be randomized, had a permanent pacemaker (interfere with WATCHPAT sleep study), were currently taking alpha blockers or nitrates (interfere with WATCHPAT sleep study), had coronary artery disease or congestive heart failure or cardiomyopathy, not delivering and completing their postpartum visit at NMCS D, inability to read or understand the consent, and  $<18$  years of age.

Each subject completed a baseline questionnaire which obtained demographics, past medical, obstetrical, and surgical history, and snoring frequency. Subjects in the control group received usual prenatal care and at 3 months postpartum they completed an unattended Watch-PAT-200 sleep study.

Subjects in the treatment group completed an OSA pregnancy screening questionnaire at each time point. The questionnaire collects information on general work and sleep patterns, sleep habits, snoring and sleep apnea symptoms, and STOP-BANG score. A research coordinator drove to the patient's home to set-up the unattended sleep study at each time point with the Watch-PAT-200 devices. The next day the research coordinator picked-up the device. Watch-PAT data was downloaded on a password-protected password and analyzed with the WatchPat zzzPAT proprietary software which automatically scored the results. If there was a technical error with the sleep study the research coordinator attempted to reschedule completion of the sleep study.

The Watch-PAT-200 is an FDA-approved portable diagnostic device (6 channels: peripheral artery tone, pulse rate, oxygen saturation, actigraphy [to calculate sleep stages], body position, & snoring) used for screening, detection, and the follow-up treatment of OSA. It uses peripheral artery tonometry (PAT) finger plethysmography and standard oxygen saturation (SPO2) probe, which allows for recording of the PAT signal, heart rate, and SPO2. Sleep time is estimated with

actigraphy. Specific data obtained included: sleep stages, pRDI, pAHI, pODI (peripheral artery tonometry respiratory disturbance index [pRDI], apnea hypopnea index [pAHI], and oxygen desaturation index [pODI]), mean and lowest oxygen saturation, percent sleep time with  $\text{SPO}_2 < 90\%$ ,  $< 88\%$ ,  $< 85\%$ ,  $< 80\%$ , and  $< 70\%$ , percent rapid eye movement of sleep time (% of sleep in REM), and the mean, minimum, and maximum heart rate.

Subjects with an  $\text{AHI} \geq 5$  were referred to the sleep medicine department for evaluation and possible treatment with CPAP. Those subjects referred for to sleep medicine received education on OSA and treatment options. If CPAP was ordered a contracted durable medical equipment company representative contacted the subject and coordinated delivery and set-up of the CPAP device. Devices used were the AirSense 10 AutoSet with auto-titrated pressure ranging from 5 to 15 cm  $\text{H}_2\text{O}$ . CPAP compliance data was obtained from the durable medical equipment contractor. CPAP compliance defined as  $> 4$  hours/night for 70% of nights.

The primary outcome was the difference in APOs between the two groups. After delivery the research coordinator reviewed the medical records and recorded the rate of individual and composite APOs in both groups (defined as a composite variable which included gestational hypertension, preeclampsia, eclampsia, gestational diabetes, preterm birth, low birth weight, or stillbirth). Results were confirmed with a co-investigator who was a Maternal Fetal Medicine Obstetrician. Secondly, we examined the rate and trends in OSA in early and late pregnancy, and at 3 months postpartum (between 8 and 12 weeks), and differences in hospital costs at the time of delivery. An exploratory aim was to compare differences in APOs between subjects at high risk for OSA started on CPAP therapy in either early or late pregnancy.

Upon completion of the 3-month postpartum sleep study subjects were given a \$150 Target gift card.

**Statistical Analysis.** Descriptive and inferential statistics were used to analyze the results. A Fisher's Exact test was used to compare differences in APOs between the treatment and control group. If significant differences are found in APOs a multiple logistic regression control for significant covariates and CPAP usage. Because sleep study results were not normally distributed a Friedman's test was used to analyze differences in sleep study results at the three time points. If significant differences are found in sleep study results a post hoc Wilcoxon Ranked Sign test will be used to compare differences at individual time points. Differences in hospital costs at the time of delivery were analyzed with a  $t$ -test. A  $P < .05$  was considered significant.

**Sample Size Estimate.** Accurate effect sizes are difficult to determine given the limited research on the effect of CPAP on APOs. We estimate that initiation of CPAP in the treatment group will reduce their risk of APOs by 20%. Using G\*Power 3.1.9.2 and a one-sided Fisher's exact test with an alpha of 0.05 and power of 80%, and a 2 to 1 allocation of control: treatment group, we would need 55 subjects in the treatment group and 110 in the control group ( $N = 165$ ). Over a 36-month data collection period we originally estimated we could enroll up to 30 subjects per quarter for a total of  $N = 360$  by the end of data collection ( $N = 180$  in each group). Subjects will be randomized to one of the two groups in a 1:1 ratio. Assuming 30% of subjects in the treatment group require CPAP initiation during their pregnancy this will give us at approximately  $N = 55$  subjects who received CPAP during pregnancy and up to  $N = 180$  control subjects. These

enrollment estimates thus meet our sample size calculation and approximate 2:1 allocation plan for analysis.

The sample size estimate of was revised 18 January 2018 and approved by CDR [name]. Our new sample size estimate was based on a 20% difference in adverse pregnancy events would be  $N = 180$  (144 in control group and 36 in treatment [CPAP group]). The plan was to continue enrollment until January 2019. The reason for stopping in January is because of the 9-month follow-up period, which would take us to September 2019. We estimated that we could enroll between 11-14 patients per month which would give us an estimated sample size at the end of active recruitment of  $N = 252$  to 288 subjects (126 to 144 per group). If we assume 25% in the treatment group have OSA, then we estimate we will have 32 to 36 subjects in the treatment group who will require CPAP therapy, meeting our target sample size.

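### The primary test ignores entry factors that shape the composite, two components lack at-risk denominators, and the only planned adjustment depends on a significant result

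*Combined protocol and SAP*

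**What the plan says.** All references are to the Combined protocol and SAP, Research Design and Methodology.

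- **Entry criteria.** A woman qualifies with one or more OSA risk factors. Besides obesity these are "chronic hypertension, pregestational diabetes, twin gestation, or a history of prior pregnancy affected by: preeclampsia, eclampsia or fetal growth restriction".
- **Primary outcome.** The composite is "defined as a composite variable which included gestational hypertension, preeclampsia, eclampsia, gestational diabetes, preterm birth, low birth weight, or stillbirth". After delivery the coordinator "recorded the rate of individual and composite APOs in both groups". No component is restricted to women who could develop it. No rule says whether a twin pregnancy counts once or per infant.
- **Statistical Analysis.** "A Fisher's Exact test was used to compare differences in APOs between the treatment and control group". No strata are named. Adjustment is conditional: "If significant differences are found in APOs a multiple logistic regression control for significant covariates and CPAP usage".
- **Sample Size Estimate.** Randomization is 1:1 with no stratification factor stated. The calculation uses a "one-sided Fisher's exact test with an alpha of 0.05 and power of 80"%. The revised plan expects 126 to 144 women per randomized group.

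**The concern.** Three of the entry factors bear directly on which components a woman can have, or how readily.

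By the ordinary meaning of the terms, a woman who already has hypertension cannot acquire gestational hypertension, and one who already has diabetes cannot acquire gestational diabetes. As written, each still sits in the denominator of that component as event-free, so the reported rate is not a rate among women at risk. A twin pregnancy is likely to reach preterm birth or low birth weight far more often than a singleton one, whichever arm it is in.

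A test that ignores strong baseline predictors gives up precision and leaves chance imbalance in them uncorrected. Here the adjusted model is fitted only when the unadjusted result is already significant, which is when it is least needed. It also conditions on CPAP usage, which arises after randomization and is largely a consequence of assignment, so it does not estimate the effect of the randomized strategy.

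**Working it through.** **1. The plan's own figure.** The original N = 165 (110 control, 55 treated) cannot be rebuilt from stated inputs, because no control rate is given; the plan says "Accurate effect sizes are difficult to determine given the limited research on the effect of CPAP on APOs". If the 20% is an absolute difference, exact one-sided Fisher power at 110/55 is 80.4% for 40% versus 20%. The revised 144/36 gives 80.0% for 30% versus 10%. So no event rate or risk-factor mix can be taken from the plan, and everything in steps 3 to 7 is illustration.

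**2. Validity of the pooled test.** Exact one-sided type I error of the Fisher test at 110/55 is 3.1-3.5% for common rates of 30-60%. Simulated two-sided rejection under the null, with twins mixed in and 126-144 per arm, is 3.4-4.2%. Pooling does not inflate error.

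**3. Component denominators.** Reported rate = rate among women at risk × (1 − share not at risk). With an assumed 18% gestational diabetes rate among women at risk:
- 10% with pre-existing diabetes: 18% × 0.90 = 16.2%
- 20% with pre-existing diabetes: 18% × 0.80 = 14.4%

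**4. Dilution, if twins do not respond (assumed).** Pooled difference = (1 − twin share) × 20 points:
- 5% twins: 0.95 × 20 = 19 points
- 10% twins: 0.90 × 20 = 18 points
- 20% twins: 0.80 × 20 = 16 points

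**5. Chance imbalance.** The SD of the between-arm difference in twin share is √(2 × f(1 − f)/n). With f = 10%:
- n = 126: √(2 × 0.09/126) = 3.8 points
- n = 144: √(2 × 0.09/144) = 3.5 points

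Multiply by the assumed gap between twin and singleton control rates (70 − 45 = 25 points, or 85 − 45 = 40). One SD of imbalance moves the composite difference by 0.035 × 25 = 0.9 to 0.038 × 40 = 1.5 points.

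**6. Power gained by stratifying on twin status.** Assumptions: singletons 45% versus 25%, twins 70-85% in both arms, 126-144 per arm, two-sided 0.05. The fair comparator is an unstratified score test, because part of any gain over Fisher is only Fisher's conservatism.

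| Twin share | Fisher | Unstratified score | Stratified Mantel-Haenszel | Gain over score test |
|---|---|---|---|---|
| 10% | 80-86% | 83-88% | 86-91% | about 1.5-4 points |
| 20% | 68-75% | not tabulated | 77-86% | about 4-7 points (up to 8 in one set of runs) |

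At 5% twins the gain is about 1-2 points. A one-sided check at the plan's CPAP-subset sizes (others 50% versus 30%, twins 80%, 10% twins) goes from 72.8% to 73.4% at 110/55, and from 61.3% to 64.4% at 144/36. If the twin rate is only 60%, there is no gain at 110/55 (73.1% against 72.5%): the benefit depends on twins being strongly prognostic.

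**7. A smaller arm-level effect.** The plan says that starting CPAP will "reduce their risk of APOs by 20"%, and expects 25-30% of the treatment group to need it. If only those women benefit, and 20% means 20 points, the arm-level effect is 0.25 × 20 = 5 to 0.30 × 20 = 6 points. At 5 points, Fisher power is 8-10% with 10-20% twins, and stratifying adds under 1 point over the score test.

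**The case against.** The case for leaving the plan alone is substantial. These women were chosen for OSA risk, which suits a trial of OSA screening. Randomization balances the factors in expectation, and the test's error rate already allows for chance imbalance. The component denominators shrink both arms' rates alike in expectation, so the relative comparison is unchanged. The power gain is small like for like, and close to nothing if benefit is confined to women who receive CPAP; women who never receive CPAP are then the larger source of dilution. All of this stands, and it limits the size of the point.

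Four stronger readings are tempting, and the documents support none of them:

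- **That women with pre-existing disease are guaranteed successes on the composite.** Each condition removes one of seven components. A woman with hypertension can still have gestational diabetes, preeclampsia, preterm birth, low birth weight or stillbirth; a woman with diabetes can still have gestational hypertension.
- **That the overlap biases or invalidates the primary test.** Step 2 shows that it does not.
- **That twins cannot benefit.** The plan gives no twin share, twin event rate or twin effect, and the composite includes disorders that a twin pregnancy can develop like any other.
- **That stratifying would restore the diluted effect.** It removes between-stratum variance; women who do not respond still dilute the average.

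The objection does not answer the conditional adjustment. After a null result no planned analysis uses the entry factors, and after a significant one the model also contains a post-randomization variable. Nor does it supply the missing denominators or the rule for counting twins.

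**Conclusion.** The point holds as a matter of efficiency and reporting, and is worth changing because the change is cheap. Three facts come from the document alone: the overlap between entry criteria and components, the single unstratified test, and an adjustment that waits for significance and includes CPAP usage. That the two pre-existing conditions exclude their gestational counterparts rests on the ordinary meaning of the terms.

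The size is modest and rests on assumed rates and shares: a few power points under a 20-point arm-wide effect (step 6), under one point if the arm-level effect is nearer 5, and component rates understated in proportion to the share of women not at risk. How strongly twin pregnancy predicts the outcome is also an assumption. The denominators and the twin-counting rule are needed whatever those rates turn out to be.

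**What to change.** 1. Make the primary comparison of the randomized groups a Mantel-Haenszel test, or its exact stratified version. Stratify by twin versus singleton and by pre-existing hypertension or diabetes (yes/no). Run it whatever the unadjusted result, without CPAP usage as a covariate.
2. Report gestational hypertension among women without chronic hypertension, and gestational diabetes among women without pregestational diabetes.
3. Report preterm birth and low birth weight separately for singleton and twin pregnancies, counted per woman, and state how a twin pregnancy in which only one infant qualifies is scored.

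**Cost.** Wording in the analysis section only. The stratification factors must be known to establish eligibility, so no new data or patients are needed. The downside is that some of the four strata may be sparse, twins with pre-existing disease most of all. A collapsing rule fixed before outcomes are compared, or the exact version, deals with that.

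### The follow-up APO regression adjusts for CPAP usage, which arises after randomization, is part of the treatment strategy and marks OSA, so it estimates neither the strategy effect nor, in general, the CPAP effect

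*Combined protocol and SAP*

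**What the plan says.** The primary comparison is Fisher's "Exact test was used to compare differences in APOs between the treatment and control group". The Statistical Analysis section then adds a conditional step: "If significant differences are found in APOs a multiple logistic regression control for significant covariates and CPAP usage". It does not say what this model is meant to estimate, whether randomized arm is a term in it, or how CPAP usage is coded (started, hours used, or the compliance definition given under Research Design and Methodology).

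The design text shows where CPAP comes from. Treatment-arm women have sleep studies, and those with an AHI of at least 5 "were referred to the sleep medicine department for evaluation and possible treatment with CPAP". Referral brings more than CPAP: "Those subjects referred for to sleep medicine received education on OSA and treatment options". For the other arm, "Subjects randomized to the control group received usual standard prenatal care", and their only study sleep test comes after delivery: "Control group subjects completed an unattended sleep study at 3 months postpartum". On CPAP data, the text says only that "CPAP compliance data was obtained from the durable medical equipment contractor".

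**The concern.** The randomized intervention is a strategy of testing, referral, education and possible CPAP. CPAP usage is a downstream part of that strategy, not a baseline characteristic, and it also identifies women found to have OSA. Conditioning on it causes two problems.

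- **The arm term loses its randomized meaning.** With both terms in the model, it compares treatment-arm non-users, mostly without OSA, with all controls, who are a mixture of women with and without OSA.
- **The CPAP term is confounded by OSA.** It compares women with OSA who use CPAP with women who mostly do not have OSA. Leaving arm out only adds the controls to the comparison group.

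OSA in pregnancy is not measured in controls, so no direct adjustment for it can restore comparability. This is also the only adjusted model planned for the primary outcome, and it runs only after a significant Fisher test. Its odds ratios would therefore be read as explaining a positive trial. They could show a useful therapy as harmful or ineffective, or present an arm effect that is not the randomized one.

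**Working it through.** The plan gives no figure for this regression, so there is none to reproduce. The one related count does reproduce: 25% of 126 to 144 women is 31.5 to 36, against the stated 32 to 36 CPAP users (Sample Size Estimate).

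**Inputs from the plan.** The OSA share comes from the revised estimate ("If we assume 25% in the treatment group have OSA"). The effect is 20%, read here as 20 percentage points because the plan does not say absolute or relative. The arm size is 144, the upper end of the revised projection.

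**Assumptions not in the plan.** The control APO rate is 40%. Every treatment-arm woman with OSA uses CPAP, and no control does. CPAP use is binary and arm is in the model. There are no other covariates. RR is the APO risk ratio for untreated OSA against no OSA.

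**Formulas.**
- Risk without OSA: n = 0.40 / (0.75 + 0.25 × RR). Untreated OSA risk = RR × n. User risk u = RR × n − benefit.
- True strategy OR = odds(0.75n + 0.25u) / odds(0.40).
- Model arm OR = odds(n) / odds(0.40). Model CPAP OR = odds(u) / odds(n). With these three cells the arm + CPAP model is saturated, so these are its exact large-sample values.
- True CPAP OR = odds(u) / odds(RR × n).
- Without an arm term, the comparison risk is (0.40 + 0.75n) / 1.75.

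| Scenario | n | OSA risk | u | Strategy OR, true | Arm OR, model | CPAP OR, true | CPAP OR, model |
|---|---|---|---|---|---|---|---|
| 1. RR 1, 20-point benefit | 0.400 | 0.400 | 0.200 | 0.81 | 1.00 | 0.375 | 0.375 |
| 2. RR 1.5, no CPAP effect | 0.356 | 0.533 | 0.533 | 1.00 | 0.83 | 1.00 | 2.07 |
| 3. RR 1.5, 20-point benefit | 0.356 | 0.533 | 0.333 | 0.81 | 0.83 | 0.44 | 0.91 |
| 4. RR 2, 20-point benefit | 0.320 | 0.640 | 0.440 | 0.81 | 0.71 | 0.44 | 1.67 |

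Worked example, scenario 2: n = 0.40 / 1.125 = 0.3556, with odds 0.5517. OSA risk is 0.5333, with odds 1.1429. Control odds are 0.6667. Arm OR = 0.5517 / 0.6667 = 0.83. CPAP OR = 1.1429 / 0.5517 = 2.07.

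The CPAP term is right only in scenario 1, where OSA has no bearing on APO, and there the arm term shows no benefit although the strategy works. The arm OR does not depend on what CPAP does: it is 0.83 in both scenarios 2 and 3. In scenario 3 it lies near the true 0.81 by coincidence.

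**No arm term.** Scenario 2: comparison risk (0.40 + 0.2667) / 1.75 = 0.381, CPAP OR 1.86. Scenario 4: (0.40 + 0.24) / 1.75 = 0.366, CPAP OR 1.36. The direction of the error is the same.

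**Sensitivity.**
- Scenario 2, half uptake: non-user risk is (0.75 × 0.3556 + 0.125 × 0.5333) / 0.875 = 0.381, so arm OR is 0.92 and CPAP OR 1.86.
- Scenario 2, control rates of 30% to 50%: arm OR 0.85 to 0.80, CPAP OR 1.83 to 2.50.
- Scenario 4, half uptake: non-user risk is (0.75 × 0.32 + 0.125 × 0.64) / 0.875 = 0.366, so CPAP OR is 1.36 against a true 0.44.

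**Allowing for the Fisher condition.** This used 200,000 simulated trials per scenario, 144 per arm, a two-sided Fisher test at P < .05, then a Wald test of the CPAP term.
- Scenario 2: Fisher is significant in about 3.6% of trials. The CPAP term is then significantly harmful in about 46% of those, or 1.7% of all trials.
- Scenario 3: Fisher favours treatment in about 11% of trials. Among those, the CPAP OR exceeds 1 in 40%, and CPAP is significantly beneficial in only 3%.
- Scenario 4: Fisher favours treatment in about 11% of trials. Among those, the CPAP OR exceeds 1 in 89% and is significantly harmful in about 25%.

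**The case against.** - **No estimand is claimed.** The plan never calls the regression output a strategy effect or a CPAP effect, and the model may be only explanatory. That is so. But an explanatory CPAP coefficient is still confounded by OSA, and a reader of the results would take it as a CPAP effect.
- **Covariates are ignored in the figures.** Snoring frequency and medical history are collected from everyone at baseline, and BMI, chronic hypertension and diabetes are eligibility factors. They are partial proxies for OSA in both arms and could shrink the bias. This stands as a limit on the sizes. The proxies do not measure OSA, and the plan does not guarantee that they enter the model.
- **The sizes rest on chosen inputs.** Full uptake is an upper bound, since CPAP is only possible after referral. At half uptake, significant false harm among Fisher-significant trials in scenario 2 falls from about 46% to 21%. In scenario 4, Fisher favours treatment in only about 5% of trials, and about 9% of those show significant false harm. This also stands: the size varies widely, and the CPAP term can keep the right direction, as in scenario 3.
- **The analysis set is not beyond doubt.** The Sample Size Estimate counts 144 controls against 36 CPAP recipients. If the Fisher test were run on those groups, arm and CPAP start would coincide, the model above would not apply, and OSA confounding would reach the primary test itself. The Statistical Analysis wording favours comparison by arm, which is the reading used here.
- **The consequence is limited.** The regression cannot change the primary test and runs only after a significant one. That limits the severity but does not make the model valid.

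**Conclusion.** The concern holds. Adjusting for CPAP usage conditions on part of the randomized strategy and on a marker of OSA that is not measured in controls during pregnancy. The arm term is then not the strategy effect. The CPAP term equals the CPAP effect only if OSA, and whatever drives uptake, is unrelated to APO or fully adjusted for. The trial's own rationale, reducing APOs by treating OSA, makes the first of these unlikely, and the design cannot deliver the second.

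This follows from the design and is held with high confidence. The size is less certain. Across the four full-uptake scenarios, the modelled CPAP OR runs from correct (0.375) to reversed (1.67 against 0.44), and a CPAP with no effect appears harmful at 2.07. These figures rest on an assumed 40% APO rate, assumed OSA risk ratios, binary CPAP use and no covariates. The primary Fisher comparison by randomized arm is not affected, so this should be fixed but does not undermine the main test.

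**What to change.** Remove CPAP usage from the regression. State that APO will be modelled on randomized arm with a prespecified list of covariates measured before randomization; the baseline questionnaire already supplies candidates.

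Report any analysis of CPAP use separately, labelled exploratory, with the coding of use, the comparison group and the assumptions about OSA and adherence written down.

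A complier-average estimate (arm risk difference divided by the between-arm difference in CPAP start) could be added as supportive only. It assumes that testing, referral and education act on APO only through CPAP, which the design makes doubtful. It also assumes that controls do not use CPAP, which would need checking because the equipment contractor is the only CPAP data source described.

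The cost is one or two sentences in the Statistical Analysis section. The arm model needs no new data.

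### Delivery hospital costs are compared by an unadjusted t-test; adjusting for the entry risk factors would sharpen the comparison at almost no cost if those factors predict cost

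*Combined protocol and SAP*

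**What the plan says.** The paragraph on outcomes lists "differences in hospital costs at the time of delivery" among the secondary aims. The Statistical Analysis paragraph gives the method: "Differences in hospital costs at the time of delivery were analyzed with a" t-test. That sentence names no covariates and does not say which groups are compared. No other economic analysis is described.

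The only covariate-adjusted model in the plan concerns adverse pregnancy outcomes (APOs), and it is conditional: "If significant differences are found in APOs a multiple logistic regression control for significant covariates and CPAP usage". It does not extend to cost.

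The inclusion criteria in Research Design and Methodology require at least one risk factor. They name "pre-pregnancy BMI" with a threshold of 30 kg/m², and "chronic hypertension, pregestational diabetes, twin gestation, or a history of prior pregnancy affected by: preeclampsia, eclampsia or fetal growth restriction". The same section adds, for both arms: "Each subject completed a baseline questionnaire which obtained demographics, past medical, obstetrical, and surgical history, and snoring frequency". The Sample Size Estimate gives 1:1 randomization and, after the January 2018 revision, projects 126 to 144 women per arm. Stratification is not mentioned.

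**The concern.** Eligibility deliberately mixes women whose expected delivery costs may differ widely whichever arm they are in, such as a singleton pregnancy admitted on BMI alone and a twin pregnancy. A t-test leaves all of that spread in the error term. To the extent that the entry factors explain cost, the interval for the cost difference is wider than it need be.

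Precision is scarce for this outcome because the contrast between arms is diluted. The revised Sample Size Estimate assumes that 25% of the treatment arm will need CPAP. If cost changed only in those women (an assumption), a difference between arms of 0.33 to 0.35 SD would require a change of about 1.3 to 1.4 SD among them (0.330/0.25 and 0.353/0.25). Adjustment does not remove that difficulty, but it is an improvement that needs no further recruitment.

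**Working it through.** **The plan's own figure.** There is none to reproduce. The documents give no cost SD, target difference, power or sample size for this outcome. The Sample Size Estimate concerns APOs and does not bear on cost.

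**Inputs from the documents.** 126 to 144 women per arm (projected enrolment), 1:1 randomization, and a significance threshold of 0.05.

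**Assumptions.** A two-sided test, since the plan does not state the sides of the t-test; a comparison of the randomized arms; and R², the share of cost variance explained by the entry factors, over a range that includes zero.

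**Step 1: the t-test.** The difference detectable with 80% power is (1.96 + 0.84) × sqrt(2/n) SD. This is 0.353 SD at n = 126 and 0.330 SD at n = 144.

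**Step 2: the adjusted comparison.** The standard error is multiplied by sqrt(1 - R²). For a difference that the t-test detects with 80% power, adjusted power = Φ(2.80/sqrt(1 - R²) - 1.96).

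| Assumed R² | SE ratio | Power | Detectable difference, n = 126 | n = 144 |
|---|---|---|---|---|
| 0 | 1.000 | 80% | 0.353 SD | 0.330 SD |
| 0.05 | 0.975 | 82% | 0.344 SD | 0.322 SD |
| 0.10 | 0.949 | 84% | 0.335 SD | 0.313 SD |
| 0.20 | 0.894 | 88% | 0.316 SD | 0.295 SD |
| 0.25 | 0.866 | 90% | 0.306 SD | 0.286 SD |

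At R² = 0.20, 126 women per arm give the precision of about 126/0.80 = 158 per arm without adjustment.

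**Step 3: what twins alone might contribute.** Let t be the twin share, k the ratio of twin to singleton mean cost, and c the within-group coefficient of variation. Then R² = t(1 - t)(k - 1)² / [t(1 - t)(k - 1)² + (1 - t)c² + t(kc)²]. All three inputs are assumed.
- Low end (t = 0.05, k = 2, c = 1.0): 0.0475/(0.0475 + 0.95 + 0.20) = 0.04.
- With k = 2 and c = 1.0, raising t to 0.10 or 0.15 gives 0.065 or 0.08.
- High end (t = 0.15, k = 4, c = 0.5): 1.1475/(1.1475 + 0.2125 + 0.60) = 0.59.

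A gain of 5 points from 80% power needs R² of about 0.125. The range falls on both sides of that value.

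**Step 4: a check with skewed costs.** Lognormal costs were simulated with assumed covariate effects giving R² of about 0.20, using robust standard errors in the adjusted model. The SE ratio was about 0.91. Power rose from 50% to 58% at 126 per arm and from 55% to 64% at 144. Type I error lay between 4.6% and 5.9% across both methods, so neither was materially off 5%.

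**The case against.** The strongest reply is that nothing in the plan is wrong. Under 1:1 randomization the t-test gives an unbiased mean cost difference, and the simulation shows acceptable type I error even with skewed costs. That stands: the point is about efficiency on a secondary outcome with no stated power target.

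A reader might infer that a chance excess of twins in one arm biases the result. It does not. At an assumed 10% twin share, the between-arm difference in that share has an SD of sqrt(2 × 0.1 × 0.9/n), or 3.5 to 3.8 percentage points. The t-test's standard error already carries that variation, so it belongs to the precision point and is not a second harm. Nor can one say that stratification was excluded; the text simply does not describe it.

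A reader might also infer that precision is certainly lost, or that a rise from 80% to 90% is the expected gain. The documents support neither. They present the entry factors as risk factors for OSA and give no cost SD, twin share, cost ratio or R². They do not say whether hospital costs include newborn care, which affects how much twins matter. The gain could be about 2 points or nothing.

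Two further objections shape the fix. First, the cost sentence does not name its groups, while the Sample Size Estimate plans an analysis of CPAP-treated women against controls. If cost followed that contrast, the detectable difference would be about 0.52 SD (36 v 144) to 0.55 SD (32 v 126), and adjustment for entry factors would not make it a randomized comparison. Second, the cost sentence is in the past tense, so an adjusted analysis added now may be post hoc.

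**Conclusion.** The point holds as a conditional, low-cost improvement. The planned t-test is valid for the randomized arms but uses none of the entry risk factors. From 80% power, adjustment adds about 2 points at R² = 0.05, 4 at 0.10, 8 at 0.20 and 10 at 0.25, and nothing at zero. These figures rest on a two-sided 0.05 test, on the randomized arms being compared, and on an R² that the documents do not supply. The 126 to 144 per arm are enrolment projections; fewer women with cost data would raise the detectable differences but leave the SE ratios unchanged.

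**What to change.** State that cost is compared between the randomized arms. Fit a linear regression of delivery cost on arm plus a pre-specified set of pre-randomization factors: twin pregnancy, pregestational diabetes, chronic hypertension, pre-pregnancy BMI, and earlier preeclampsia, eclampsia or growth restriction. Use heteroscedasticity-robust or bootstrap standard errors and report the adjusted mean difference with its 95% CI. Report the unadjusted t-test difference alongside.

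Use no post-randomization variable, such as AHI, CPAP use or gestational age at birth, and do not select covariates by significance. If the model is specified after costs were seen, label it post hoc.

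Entry needs only one factor, and twin status and BMI are not listed as questionnaire items, so confirm that all the factors are recorded for every woman. Otherwise the change costs a sentence of analysis text, a few lines of code, and a few degrees of freedom for about five covariates among a projected 252 to 288 women.
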